#### Secondary objectives:

- 1. To examine the correlation between postprandial exhaled hydrogen and methane (H2) content as measured over a 1-week period by AIRE on the patient's usual diet at home and the results of the standardized LHBT performed in the clinic
- 2. To examine the correlation between AIRE results and gastrointestinal symptoms suggestive of SIBO
- 3. To examine the response of hydrogen and methane breath concentrations using AIRE to antibiotic treatment (in patients undergoing antibiotic treatment).
- 4. To assess the reproducibility of the AIRE results over several weeks in patients not undergoing antibiotic treatment.
- 3. Background (briefly describe pre-clinical and clinical data, current experience with procedures, drug or device, and any other relevant information to justify the research) Small intestinal bacterial overgrowth (SIBO) is defined as a condition in which an abnormally high amount of coliform bacteria is present in the small bowel and results in premature anaerobic fermentation of carbohydrates before reaching the colon. Commonly recognized causes include gastric achlorhydria (ie due to longstanding PPI use), post-surgical bowel stasis, and gastrointestinal motility disorders leading to bowel stasis. Although SIBO is commonly suspected, a major limitation in the field is the lack of a highly accurate test for SIBO. The current gold standard relies on the demonstration of an early rise in breath hydrogen concentration in response to an orally ingested carbohydrate (commonly, lactulose) but its accuracy is about 50%. This may be because it is a one-time snapshot with an artificial substrate. Further, it has to be performed in a clinic, takes up to 5 hours and is relatively expensive. The purpose of this study is to evaluate the clinical utility of a portable medical device called AIRE, which is a validated and commercially available handheld breathalyzer that measures hydrogen and methane content in the breath and connects via Bluetooth to an associated smartphone application to provide immediate results and

Principal Investigator: [name]

Application Number: IRB00204104

visual feedback after use. H2 concentrations determined by the AIRE device showed significant correlation with those measured by LHBT. The AIRE device therefore provides an alternative way to measure exhaled H2 and methane that have the potential for addressing many of the limitations of the standard breath test.

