#### **Study Procedures**

This pilot study will be an open-label trial in patients suspected to have SIBO (abdominal bloating, distention, discomfort, change in bowel movements) and who are being considered for diagnostic testing using the lactulose-hydrogen breath test (LHBT). 150 patients will be accrued from the gastroenterology motility clinic or the scleroderma clinic, in addition, 20 healthy volunteers will be accrued making a grand total of 120 participants. Healthy volunteers will be recruited initially at the Ross Research Building. Other alternatives provided by The Recruitment Innovation Unit (RIU) from the Institute for Clinical & Translational Research (ICTR) Johns Hopkins Medicine may be considered to make our study more visible within Hopkins community. If the subject meets eligibility criteria, and the LHBT has been scheduled, a co-investigator will contact the patient to schedule a study visit with a research coordinator and obtain a written consent. Potential subjects will be provided with a copy of the Informed Consent form prior to the remote consent meeting either via email, fax, mail or previously provided during an in person visit. Potential subjects will then be contacted by phone by a study team member who is a consent designee to review the consent form in detail. Potential subjects will be given adequate time to consider the research study and ask questions prior to signing the consent form. The potential subject will then sign and date/time the informed consent document and it will be mailed, emailed or faxed to the consent designee, who will also sign/date/time. A copy of the fully signed consent form will be returned to the volunteer. The contact and screening information of patients that are successfully recruited will be documented, placed in the participant's study folder and stored in a locked cabinet in the motility clinic at Bayview. Any information documented during the screening process for patients who do not meet basic eligibility criteria or do not wish to participate will be immediately destroyed.

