Healthy volunteers will be asked the Gastrointestinal Symptom Rating Scale (GSRS). This instrument address 15 items combined into five symptom clusters: Reflux, Abdominal pain, Indigestion, Diarrhea and Constipation. The reliability and validity of the GSRS are well-documented, and norm values for a general population are available. The original questionnaire is an interview-based rating scale but has been modified to become a self-administered questionnaire. Takes approximately 3-5 minutes Recall period is past week. Each item is rated on a 7-point Likert scale.

Following a week of AIRE measurement, participants will then undergo the physician-ordered and clinically indicated LHBT done on the clinically scheduled day and time. They will use the AIRE device one time immediately before the LHBT begins and throughout the lactulose breath test as well, at the same intervals as the lactulose breath test (breathe into AIRE device immediately after breathing into the standard lactulose breath test tube).

Subjects will be notified of the breath test result and whether or not they will receive antibiotics. This will be the only result for disclosure to the participant. Decisions regarding treatment will be based on clinical judgment and standard of care, after taking into consideration the patient's history and test results. This decision will be made by the care provider (MD or mid-level) and will be discussed with the patient by a member of the study team.

A Lactulose challenge using the AIRE device will be repeated after 5 - 7 days of the initial LHBT if this reports negative findings for SIBO. We are testing the hypothesis that repeating the test will increase the probability of a positive response.

If subjects receive antibiotic treatment, they will be asked to use the AIRE device three days before they begin taking antibiotics, during treatment, and for four weeks after treatment ends.

One month later (if no antibiotics were prescribed) participants will repeat the 1-week use of AIRE device described above. Therefore, all participants will complete this second week of AIRE use regardless whether or not they received antibiotics. A second round of antibiotics will be prescribed if the patient does not response to the initial treatment based on the attending physician decision.

Once the second week of AIRE use is completed, participants will return the AIRE machine. Data from the app is automatically downloaded from the app to the Food Marble server.

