#### 6. Study Statistics—

This study is powered around the primary objective i.e. to examine the correlation between postprandial exhaled hydrogen (H2) content as measured over a 1-week period by AIRE on the patient's usual diet at home and the results of the standardized lactulose hydrogen breath test (LHBT) performed in the clinic. We predict a moderate correlation between these two tests and assuming an alpha-error of 0.050 and a beta error of 0.200, 100 patients will be sufficient for an expected correlation coefficient of 0.5.

We are requesting this because although the original aim (comparison to a commercial test) has been almost completed, an initial look at the data also shows that we may be picking up additional signals from day to day breath testing that could be a biomarker for the response to antibiotics. This will however require additional patients since only about 30% of patients are responders (exemplifying the need for more accurate tests for SIBO); we estimate that by doing 70 more patients we will get about 20 more responders bringing the total number of responders to about 30, which may give us enough power to test this emerging hypothesis. We will do a formal interim analysis of this about halfway through the additional recruitment target and reassess the need to continue at that point.

In order to interpret the postprandial breath readings of SIBO patients it can only be done properly when compared to normative data. We estimate that 20 healthy volunteers with a proportion of 60% women and 80% between 18 and 40 years old will be enough to compare and interpret postprandial H2 readings.

In addition to the initial 100 patients and 20 healthy volunteers we want to accrued 50 patients to examine the correlation of pre and postprandial Methane breath using the AIRE device and compare also with a LHBT.

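### The repeat-challenge hypothesis is tested only in LHBT-negative patients with no named comparator, so measured against the first LHBT it cannot fail

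*Combined protocol and SAP*

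**What the plan says.** Study Procedures says that a lactulose challenge "using the AIRE device will be repeated after 5 - 7 days of the initial LHBT if this reports negative findings for SIBO". The purpose follows: "We are testing the hypothesis that repeating the test will increase the probability of a positive response". No repeat LHBT is described, and no rechallenge of LHBT-positive patients.

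The same section provides for AIRE readings at the first test: "They will use the AIRE device one time immediately before the LHBT begins and throughout the lactulose breath test as well". These are taken at the LHBT's own intervals. Every retested patient should therefore have a first AIRE lactulose curve.

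The Background says that the field lacks a highly accurate test for SIBO. Of the LHBT it says that "its accuracy is about 50%. This may be because it is a one-time snapshot with an artificial substrate".

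The repeat-challenge hypothesis is not among the primary or secondary objectives, and section 6 (Study Statistics) does not mention it. The documents give it no comparator, AIRE cut-off, analysis or sample size. On enrolment, Study Procedures says "150 patients will be accrued from the gastroenterology motility clinic or the scleroderma clinic". It does not limit the rechallenge to a subgroup, nor say from which patient on it applies.

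**The concern.** The selection rule decides the direction of the result. Everyone retested has just had a negative LHBT, so on that scale the group starts at 0% positive. Any test that is less than perfectly repeatable will then turn some of them positive. The opposite flow, from positive to negative, is never observed, because LHBT-positive patients are not retested. An apparent confirmation would follow even if repeating the challenge had no effect.

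What is at stake is the meaning of the result. Extra positives after a negative first test may be missed SIBO, false positives or day-to-day variation. If the repeat AIRE result is set against the first LHBT result, they may also be disagreement between the two devices. The plan fixes no comparison that would narrow this list.

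**Working it through.** The plan has no figure of its own to reproduce here. Its one complete sample-size statement (100 patients, correlation 0.5) concerns the AIRE-LHBT correlation and does not bear on this point.

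**Inputs.** From the documents: 150 patients, retest only if the LHBT is negative, LHBT accuracy about 50%. Assumed: LHBT-positive proportion q of 30-50%, equal cut-offs, normally distributed readings, no true repeat effect, and the correlations shown.

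**1. Repeat AIRE against first LHBT.** With t the cut-off that leaves a proportion q above it, and Φ₂ the bivariate normal distribution function:

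P(AIRE2+ | LHBT1−) = 1 − Φ₂(t, t; r) / (1 − q)

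Expected conversions are 150 × (1 − q) × that probability.

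| r | q = 30% (105 negatives) | q = 40% (90) | q = 50% (75) |
|---|---|---|---|
| 0.9 | 8.9%, 9.4 patients | 11.6%, 10.4 | 14.4%, 10.8 |
| 0.7 | 15.6%, 16.4 | 20.4%, 18.4 | 25.3%, 19.0 |
| 0.5 | 20.5%, 21.5 | 26.8%, 24.1 | 33.3%, 25.0 |

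So 9-33% convert with no true effect. Under the same model 14-48% of LHBT-positives would turn negative on a repeat (14.4% at q = 50%, r = 0.9; 47.7% at q = 30%, r = 0.5). The design does not see that flow.

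**2. Repeat AIRE against first-sitting AIRE, among LHBT-negatives.** This removes the device switch. Selection on the LHBT still matters if AIRE tracks a same-sitting LHBT more closely than one 5-7 days away:

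Rise = P(AIRE2+ | LHBT1−) at the between-day r, minus P(AIRE1+ | LHBT1−) at the same-sitting r

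For example, at q = 40%, 0.90 same-sitting and 0.70 between days: 20.4% − 11.6% = 8.8 points.

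| Same-sitting r / between-day r | Rise in points, q = 30 / 40 / 50% |
|---|---|
| equal | 0 / 0 / 0 |
| 0.75 / 0.70 | 1.4 / 1.9 / 2.3 |
| 0.90 / 0.85 | 2.0 / 2.7 / 3.3 |
| 0.80 / 0.70 | 3.0 / 3.9 / 4.8 |
| 0.90 / 0.70 | 6.7 / 8.8 / 11.0 |
| 0.90 / 0.50 | 11.5 / 15.2 / 19.0 |

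The bias is nil with no gap, 1-5 points for a gap of 0.05-0.10, and 7-19 points for a gap of 0.20-0.40.

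**3. True and false positives among converters.** Take sensitivity Se = specificity Sp = 0.5, one reading of an accuracy of about 50%, with repeats independent given disease and prevalence p.

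- First-test negatives: p(1 − Se) + (1 − p)Sp = 0.5p + 0.5(1 − p) = 0.5
- True converters: p(1 − Se)Se = 0.25p
- False converters: (1 − p)Sp(1 − Sp) = 0.25(1 − p)
- Conversion: 0.25 / 0.5 = 50%, at any p
- True share of converters: 0.25p / 0.25 = p

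An observed 50% conversion would thus fit a true share of 20%, 30%, 50% or 70%, depending only on prevalence. Counting any positive as positive moves sensitivity from 0.50 to 1 − 0.5² = 0.75 and specificity from 0.50 to 0.5² = 0.25.

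**The case against.** The strongest answer is that the plan already collects what is needed. AIRE is read throughout the first LHBT, so a same-device, same-patient comparison is available. A reader might infer that device disagreement is inseparable from the effect of repeating. The documents do not support that: it enters only if repeat AIRE is set against the first LHBT. Nor does it follow that the rate can never fall. That holds for cumulative or LHBT-anchored positivity, but AIRE positivity among LHBT-negatives can move either way, since some may be AIRE-positive at the first sitting. What stands is that the plan names no comparator.

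Second, yield after a negative test is a fair question when the LHBT is suspected of failing as a single snapshot, and the stated hypothesis concerns positive responses, not accuracy. A reader might infer that the trial intends to claim better detection of SIBO. No section plans that claim. The risk is that nothing rules out that reading.

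Third, the size of the remaining bias rests on assumed correlations and may be nil. That is correct.

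Fourth, the lack of a good reference standard is a limit of the field, and this is a pilot. Both are true, and they bound the importance of the point.

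The reproducibility objective, "To assess the reproducibility of the AIRE results over several weeks in patients not undergoing antibiotic treatment", does not fill the gap. Its data come from repeating the home-diet week about a month later, not from a second lactulose challenge.

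**Conclusion.** The point holds in a limited form. As written, the hypothesis cannot fail if the result is measured against the first LHBT or as cumulative positivity. The apparent conversion with no true effect is 9-33%, or about 9-25 patients if all 150 fall under the rechallenge. With the AIRE reading from the first LHBT as comparator, the device switch disappears and the bias is 0 to 19 points, small unless the same-sitting correlation clearly exceeds the between-day one. LHBT positivity, equal cut-offs, normality and all correlations are assumptions, so these are ranges and not estimates for this trial. Under either comparator, the share of converters who truly have SIBO cannot be learned from this design. The effect is confined to one claim outside the listed objectives; the correlation analyses are untouched.

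**What to change.** In the protocol and analysis plan:

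- Name the AIRE reading taken during the first LHBT as the comparator for the repeat AIRE challenge.
- Apply one AIRE positivity rule, fixed before analysis, to both sittings.
- Among LHBT-negative patients, report paired AIRE changes in both directions, with a 95% CI. As a guide to precision, a conversion proportion of 20% would have a half-width of 1.96 × √(0.16/n): about 8 points with 105 retested and 9 with 75.
- Label the item exploratory, and state which enrolled patients fall under the rechallenge.
- State that, because selection is on a negative LHBT and positives are not retested, a rise is additional yield and will not be read as improved detection of SIBO.

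The cost is wording only: AIRE is already used at both challenges, so no test, visit or patient is added. The downside is a more modest claim, and the true-SIBO share of conversions stays unknown.

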#### b. Study duration and number of study visits required of research participants.

Study duration is approximately 7 weeks with a total of 2 study visits (one initial study visit to allow for consent and to provide relevant materials, and one follow up study visit (to return materials and allow for data collection).

c. Blinding, including justification for blinding or not blinding the trial, if applicable. N/A: no blinding indicated.

Principal Investigator: [name]

Application Number: IRB00204104

## d. Justification of why participants will not receive routine care or will have current therapy stopped.

N/A: participants are not undergoing treatment related to this study.

e. Justification for inclusion of a placebo or non-treatment group.

N/A: this is not a drug study.

f. Definition of treatment failure or participant removal criteria.

Subjects can voluntarily remove themselves from a part or the entire study at any time. Subjects may also be removed from the study if:

- failure to follow instructions
- study is cancelled
- there may be other reasons to take a subject out of the study that we do not know at this time
- g. Description of what happens to participants receiving therapy when study ends or if a participant's participation in the study ends prematurely.

N/A; subjects are not undergoing any therapy related to this study.

#### 4. Inclusion/Exclusion Criteria

Subjects will be recruited from the Johns Hopkins motility disorder clinic and/or the scleroderma clinic. Inclusion criteria for this study are as follows:

#### Inclusion:

- Adults (18 years of age or older)
- Chronic (>3 months) GI symptoms such as nausea, bloating, distention, altered bowel movements, weight loss or abdominal pain with no structural cause other than scleroderma
- Clinical diagnosis of SIBO by patient's gastroenterologist with plans to obtain a lactulose hydrogen breath test
- Ability to tolerate oral intake
- Ability to undergo the LHBT
- Access to a smartphone with Bluetooth capability

#### **Exclusion:**

- History of current or recent antibiotic use within the last 30 days
- History of inflammatory bowel disease
- Currently following a restrictive diet (for example low FODMAP diet)
- Unable to tolerate oral intake

#### Criteria for Healthy Volunteers.

#### Inclusion:

- Adults (18 years of age or older)
- Ability to tolerate oral intake.
- Access to a smartphone with Bluetooth capability
- Willingness to use the AIRE device at the first and last meal of the day for 8 weeks.
- Willingness to complete the GSRS questionnaire.

#### **Exclusion:**

Principal Investigator: [name]

Application Number: IRB00204104

 Patients with past or current medical history of gastrointestinal illnesses (Functional and motility disorders)

- Patients diagnosed with SIBO.
- Patient currently taking antireflux medications (Proton pump inhibitors, H2 antagonist, etc.)
- Patients following a restrictive, gluten free or FODMAP diet.
- Previous gastro-esophageal surgery including vagotomy, fundoplication, gastric bypass, ulcer surgery.
- Prior GI surgery except for uncomplicated appendectomy and laparoscopic cholecystectomy;
- Surgery within the past 3 months.
- Patients with BMI lower than 18.5 or higher than 29.9
- History of current or recent antibiotic use within the last 30 days.

#### 5. Drugs/ Substances/ Devices—

The device being tested is AIRE breathalyzer which is a validated and commercially available hydrogen breathalyzer created by FoodMarble (https://foodmarble.com/).

#### 6. Study Statistics—

This study is powered around the primary objective i.e. to examine the correlation between postprandial exhaled hydrogen (H2) content as measured over a 1-week period by AIRE on the patient's usual diet at home and the results of the standardized lactulose hydrogen breath test (LHBT) performed in the clinic. We predict a moderate correlation between these two tests and assuming an alpha-error of 0.050 and a beta error of 0.200, 100 patients will be sufficient for an expected correlation coefficient of 0.5.

We are requesting this because although the original aim (comparison to a commercial test) has been almost completed, an initial look at the data also shows that we may be picking up additional signals from day to day breath testing that could be a biomarker for the response to antibiotics. This will however require additional patients since only about 30% of patients are responders (exemplifying the need for more accurate tests for SIBO); we estimate that by doing 70 more patients we will get about 20 more responders bringing the total number of responders to about 30, which may give us enough power to test this emerging hypothesis. We will do a formal interim analysis of this about halfway through the additional recruitment target and reassess the need to continue at that point.

In order to interpret the postprandial breath readings of SIBO patients it can only be done properly when compared to normative data. We estimate that 20 healthy volunteers with a proportion of 60% women and 80% between 18 and 40 years old will be enough to compare and interpret postprandial H2 readings.

In addition to the initial 100 patients and 20 healthy volunteers we want to accrued 50 patients to examine the correlation of pre and postprandial Methane breath using the AIRE device and compare also with a LHBT.

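### Section 6 pairs alpha 0.05, beta 0.20 and r = 0.5 with 100 patients, but those inputs give about 29 to 30; the basis for 100 is not stated

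*Combined protocol and SAP*

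**What the plan says.** Section 6 (Study Statistics) says that the study is powered on its primary objective. It describes this as the correlation between one week of home postprandial hydrogen readings on AIRE and the clinic lactulose hydrogen breath test (LHBT). It continues: "We predict a moderate correlation between these two tests", and then "assuming an alpha-error of 0.050 and a beta error of 0.200, 100 patients will be sufficient for an expected correlation coefficient of 0.5". It gives no sidedness, null value, minimum acceptable correlation, type of coefficient, formula or allowance for non-evaluable patients.

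The next paragraph says that the comparison with the commercial test is nearly complete. It asks for 70 further patients so that breath readings can be studied as a marker of antibiotic response. About 30% of patients respond, so the 70 are expected to add about 20 responders and bring the total to about 30.

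A separate cohort is sized without any error rates: "we want to accrued 50 patients to examine the correlation of pre and postprandial Methane breath using the AIRE device".

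Section 2 gives a different primary objective: AIRE against LHBT when the two are done together. The home-week correlation is secondary objective 1 there.

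**The concern.** A sentence that lists alpha, beta and an expected effect and then gives a patient number reads as a sample-size derivation. A reader will take 80% as the power of the design and 100 as the number that delivers it. If the inputs give a much smaller number, the 100 rests on something that is not written down, such as a smaller expected correlation, a non-zero null, expected attrition or another aim.

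This is the only sizing statement in the plan with an explicit alpha, beta and effect. While its basis is unclear, an ethics or statistical reader cannot tell which patients serve the correlation and which serve the antibiotic-response question. Nor can they tell how precisely the correlation will be estimated.

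**Working it through.** **Inputs from Section 6.** Alpha: "assuming an alpha-error of 0.050". Beta: "a beta error of 0.200", so power is 0.80. Effect: "for an expected correlation coefficient of 0.5". Stated size: 100.

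**Assumed because not stated.** Two-sided test, null correlation zero, Pearson coefficient, no dropout.

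**1. Reproducing the stated size.** By Fisher's z, n = ((z_alpha + z_power) / atanh(r))^2 + 3.

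- atanh(0.5) = 0.5493; z_alpha = 1.960; z_power = 0.842.
- n = ((1.960 + 0.842) / 0.5493)^2 + 3 = 29.01 with unrounded inputs, so 29, or 30 if rounded up strictly.
- Simulation of the exact t test on bivariate normal data gives 79.8% power at n = 28 and 81.3% at n = 29.

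The stated 100 is not reproduced.

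**2. Power at the stated size.** Power = Phi(atanh(r) × sqrt(n - 3) - z_alpha) = Phi(0.5493 × sqrt(97) - 1.960) = Phi(3.45) = 0.9997. Beta is therefore about 0.0003. Simulation gives 99.98%.

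**3. Other readings of the same inputs (r = 0.5 throughout).**

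| Reading | n |
|---|---|
| One-sided, 80% power | 24 |
| Two-sided, 80%, Spearman variance factors | 31 to 33 |
| Two-sided, 90% power | 38 |
| Two-sided, 95% power | 47 |
| Two-sided, 80%, Bonferroni for 10 tests | 48 |
| Two-sided, 99% power | 64 |

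None comes near 100.

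**4. What would give 100.** Each of these is an input that the plan does not state.

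- A smaller expected correlation: tanh(2.802 / sqrt(97)) = 0.277 two-sided (0.247 one-sided).
- A non-zero null with true r = 0.5: tanh(0.5493 - 2.802 / sqrt(97)) = tanh(0.5493 - 0.2845) = 0.259 two-sided (0.288 one-sided).
- Attrition: 1 - 29/100 = 71%.

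**5. A match inside Section 6.** 100 - 70 = 30, the size found in step 1. The responder figures agree: 30 - 20 = 10 responders expected without the 70, and 10 / 0.30 is about 33 patients.

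**6. What 100 patients give.**

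- 95% CI at an observed r of 0.5: tanh(0.5493 ± 1.960 / sqrt(97)) = 0.34 to 0.63.
- Smallest r significant against zero, two-sided: t / sqrt(n - 2 + t^2) with t = 1.984 on 98 degrees of freedom = 0.197. That is 0.197^2 = 4% shared variance, against 0.5^2 = 25% at the predicted value.

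**The case against.** The strongest reply is that the sentence calls 100 sufficient, not necessary, and 100 exceeds 29. That is literally true and it stands. The sentence does not say in so many words that power at 100 is 80%. The plan describes a pilot whose first aim is nearly complete, and no conclusion about r = 0.5 is endangered. What remains is that the quoted error rates do not lead to the quoted number, and no other basis is given.

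A reader might also infer several stronger points that the documents do not support:

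- **That the study is underpowered.** The opposite holds for this test.
- **That all 100 patients come from the antibiotic-response extension.** Section 6 ties only 70 to it. The account in which 30 became 100 is an inference from matching figures.
- **That a zero null is already settled.** Section 3 (Background) reports that hydrogen "concentrations determined by the AIRE device showed significant correlation with those measured by LHBT". That does not establish a correlation between a week of home readings on usual diet and a clinic LHBT.
- **That the sentence makes the 50-patient methane cohort too small.** Sufficient does not mean necessary, and no expected methane correlation is stated.
- **That an r of 0.20 would be declared a success.** The plan defines no success criterion. A lower critical value is a property of any larger sample, not an error. It is a reason to report an interval, and no more than that.

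**Conclusion.** The point holds as a mismatch between the stated inputs and the stated number. About 29 to 30 patients are needed where the plan gives 100, and beta at 100 is about 0.0003 where the plan gives 0.20. The exact figures assume a two-sided test against zero with a Pearson coefficient. One-sided and Spearman versions give 24 to 33, so the conclusion does not depend on those choices. It would change only with an unstated input: an expected r of about 0.28, a null of about 0.26 (both two-sided), or about 71% loss. The likely cause, an enlarged total with an unchanged power statement, is for the sponsor to confirm. The consequence lies in what the plan tells its readers, not in the strength of the test.

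**What to change.** Replace the sizing sentence in Section 6 with text such as: *About 30 evaluable patients give 80% power (two-sided alpha 0.05) to distinguish r = 0.5 from zero. With 100 patients, power against zero is above 99.9%, power is 80% to show a correlation above about 0.26 if the true value is 0.5, and the 95% CI at an observed r of 0.5 is about 0.34 to 0.63.*

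In addition:

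- The sponsor should state the actual basis for 100, noting that Section 6 links 70 of these patients to the antibiotic-response hypothesis.
- Name the correlation being sized, and reconcile Section 6 with the primary and secondary objectives in Section 2.
- Report the correlation with its 95% CI and interpret the lower limit, since significance against zero at n = 100 needs an r of only about 0.20.
- If a methane figure is added, label it as an assumption: at r = 0.5 and n = 50, tanh(0.5493 ± 1.960 / sqrt(47)) gives about 0.26 to 0.68.

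The cost is rewording. No patients or procedures are added. The one real consequence is that a p-value against zero would no longer carry the conclusion by itself.

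### The enrolment total is given as 120 but its parts sum to 170, and the interim look at the antibiotic-response hypothesis has no stated rule for stopping or continuing

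*Combined protocol and SAP*

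**What the plan says.** On numbers, Study Procedures sets a target of 150 patients and continues that "20 healthy volunteers will be accrued making a grand total of 120 participants". Section 6 (Study Statistics) builds the same enrolment from an initial 100 patients and 20 healthy volunteers, and adds that "we want to accrued 50 patients to examine the correlation of pre and postprandial Methane breath".

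On the interim look, Section 6 reports that a first inspection of the data suggested "additional signals from day to day breath testing that could be a biomarker for the response to antibiotics". It asks for 70 more patients to pursue this. At a responder rate of about 30%, it expects these to bring about 20 more responders and a total of about 30. The next sentence commits the team to a "formal interim analysis of this about halfway through the additional recruitment target and reassess the need to continue at that point".

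The only error rates in the documents belong to a different question, the hydrogen correlation between AIRE and the lactulose hydrogen breath test (LHBT): "assuming an alpha-error of 0.050 and a beta error of 0.200, 100 patients will be sufficient for an expected correlation coefficient of 0.5". The antibiotic-response hypothesis has no stated test, significance level or effect size.

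**The concern.** There are two separate matters.

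The first is arithmetic. The grand total disagrees with its own components in the same sentence and with Section 6. Readers who take the total and readers who add up the parts arrive at enrolments that differ by 50 people.

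The second is the look at accumulating data. It is called formal and leads to a decision on whether to go on recruiting, in a study with no blinding. The plan does not say what result would stop recruitment, who decides, or whether a favourable result may be a reason to stop. It is also unclear what halfway counts: patients enrolled, patients given antibiotics, responders, or patients who have completed the four weeks of AIRE use after treatment. If a favourable look can end recruitment and the result is then reported at a nominal 5%, the true false-positive rate is higher.

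A related weakness is that the patients who suggested the hypothesis also appear to be counted in the sample that will test it.

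**Working it through.** **1. The total.** The stated figure is 120.
- It is reproduced by 100 + 20 = 120, the initial patients plus the volunteers.
- Study Procedures, own parts: 150 + 20 = 170.
- Section 6, own parts: 100 + 20 + 50 = 170.
- Difference: 170 − 120 = 50, the size of the methane group.

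**2. How the 150 patients are made up.** Inputs from Section 6: 70 more patients, 30% responders, about 20 new responders, about 30 in total, and 50 methane patients.
- New responders: 70 × 0.30 = 21, which agrees with the plan's figure of about 20.
- Existing responders: 30 − 20 = about 10.
- Existing patients: 10 / 0.30 = about 33. This is inferred; the documents do not give it.
- 33 + 70 = about 103, close to the initial 100. Then 100 + 50 = 150, the target in Study Procedures.
- If the 70 came on top of the 100, the patient target would be 100 + 70 + 50 = 220, which does not match the stated 150.

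**3. Information at the look.** Half of 70 is 35 patients, with 35 × 0.30 = about 10 new responders. Let t be the fraction of the final information available at the look, taken as proportional to patients or responders.
- New patients only: t = 35/70 = 1/2.
- Pooled patients, with about 30 already in hand: t = (30 + 35)/100 = 0.65.
- Pooled responders: t = (10 + 10)/30 = 2/3.

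**4. Error rate if both looks are tested without adjustment.** Assume two-sided 5% at each look and that significance stops accrual. The overall error is 1 − P(|Z1| < 1.96 and |Z2| < 1.96), where Z1 and Z2 are standard normal with correlation √t.

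| t | √t | Overall error |
|---|---|---|
| 1/2 | 0.707 | 8.3% |
| 0.65 | 0.806 | 7.8% |
| 2/3 | 0.816 | 7.7% |

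**5. A boundary that restores 5%.** With O'Brien-Fleming-type spending at overall two-sided 0.05, the amount spent at the look is 4 × [1 − Φ(2.241/√t)]. The final critical value is then solved from the same bivariate normal.
- t = 1/2: 2.241/0.707 = 3.170, so nominal p is 0.003 at the look and 0.049 at the end.
- t = 2/3: 2.241/0.816 = 2.745, so nominal p is 0.012 at the look and 0.046 at the end.

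**The case against.** The strongest defence of the look is that it is modest. The study calls itself a pilot, the hypothesis is described as emerging, and the request rests on a hope of having enough power. Reconsidering whether to continue may therefore mean no more than a feasibility or sample-size check. No significance level is attached to this hypothesis, so no stated level is breached. That stands, and it makes the 7.7% to 8.3% conditional. It does not remove the gap, because the text does not rule out stopping on a good result.

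On the total, 120 is easily recognised as a sum that was not updated when the methane patients were added, and the correct parts stand beside it. That also stands. A reader might infer that recruitment would actually close 50 people short, but nothing in the documents shows this; it is a contradiction to be corrected.

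Three stronger readings are tempting and are not supported:
- **That 70 and 50 are rival recruitment targets, so the look could fall at patient 35 or patient 25.** The sentence on the look directly follows the request for 70 and refers back to it. The 50 come later, for the methane question, and step 2 reconciles both figures with 150.
- **That the first inspection of the data was already a test, making three looks.** Counting it would give about 10.7% to 10.9% (information 1/3, 2/3, 1 or 0.30, 0.65, 1). The documents describe no test or stopping option at that point.
- **That limiting the look to futility would by itself justify a clean 5% final test.** It would not, because the patients who prompted the hypothesis appear to be counted in the final 30 responders.

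**Conclusion.** The enrolment total is wrong: it should read 170, and this needs no assumption. It is a clerical error, independent of the interim question.

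The interim look lacks a decision rule, a defined count and a named decision-maker. Its effect on error is about 7.7% to 8.3% in place of 5%, and only if both looks use unadjusted two-sided 5% and significance stops accrual. The documents neither state nor exclude this. The range also assumes that information accrues in proportion to patients or responders and that the look falls near 35 of the 70.

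The consequence is confined to the antibiotic-response hypothesis. The AIRE-LHBT correlation on which the study is sized is not affected. The overlap between the patients who generated the hypothesis and those who will test it rests on the inferred figure of about 10 existing responders, and it would remain whatever rule is chosen for the look.

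**What to change.** 1. In Study Procedures, change the grand total to 170 (150 patients and 20 healthy volunteers). List the increments that make up the 150, with the purpose of each.
2. In Section 6, fix the look at one stated count: for example 35 of the 70 additional patients, or a stated number of antibiotic-treated patients with complete follow-up. The second avoids counting patients who receive no antibiotics and so cannot inform the question. Name who makes the decision.
3. State that the look can stop accrual only for futility or feasibility, and give the criterion. If an efficacy stop is wanted, set an O'Brien-Fleming-type boundary: nominal p of about 0.003 at the look and 0.049 at the end for information 1/2.
4. Either test the hypothesis in the newly enrolled patients only, or report the pooled result as exploratory.

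These are wording changes that add no patients or procedures. The team gives up an unadjusted early stop on an encouraging look, and a new-patients-only test would rest on about 20 responders instead of 30.
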